  11. Patients who prematurely discontinue from trial medication will be required to return to the study site as soon as possible after treatment discontinuation for the early discontinuation visit and the follow up visit. In addition, the patient should return to clinic for their regularly scheduled week 12 study visit as outlined in [section 3.3.4.1](#).

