#### **Decreased renal function**

Decreased renal function is defined by a creatinine value showing a  $\geq 2$  fold increase from baseline and is above the Upper Limit of Normal (ULN).

For the AESI "decreased renal function" patients need to be followed up appropriately based on local clinical guidance.

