#### **7.3.4 Safety analyses**

Adverse events will be coded using the Medical Dictionary for Drug Regulatory Activities (MedDRA). Standard BI summary tables and listings will be produced. All adverse events with an onset between start of treatment and end of the residual effect period (REP), a period of 7 days after the last dose of trial medication, will be assigned to the on-treatment period for evaluation.

All treated patients will be included in the safety analysis. In general, safety analyses will be descriptive in nature and will be based on BI standards. No hypothesis testing is planned.

Statistical analysis and reporting of adverse events will concentrate on treatment-emergent adverse events, i.e. all adverse events occurring between start of treatment and end of the residual effect period. Adverse events that start before first drug intake and deteriorate under treatment will also be considered as 'treatment-emergent'.

Frequency, severity, and causal relationship of adverse events will be tabulated by system organ class and preferred term after coding according to the current version of the Medical Dictionary for Drug Regulatory Activities (MedDRA) at the database lock.

Laboratory data will be analysed both quantitatively as well as qualitatively. The latter will be done via comparison of laboratory data to their reference ranges. Values outside the reference range as well as values defined as clinically relevant will be summarised. Treatment groups will be compared descriptively with regard to distribution parameters as well as with regard to frequency and percentage of patients with abnormal values or clinically relevant abnormal values.

Vital signs, physical examinations, or other safety-relevant data observed at screening, baseline, during the course of the trial and at the end-of-trial evaluation will be assessed with regard to possible changes compared to findings before start of treatment.

Reasons for discontinuation and use of post-baseline concomitant medications will be tabulated.

The details of the analysis will be specified in the TSAP.

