## 6. GENERAL ANALYSIS DEFINITIONS

### 6.1 TREATMENTS

There will be 3 study intervals in this trial: screening, study treatment phase (with either empagliflozin 10mg or matching placebo) and follow-up. The purpose of the definitions below is to describe the different study intervals.

Table 6.1: 1 Treatment regimens / study intervals

Label in database	Label in tables and listings	Interval	Start date
SCREENING	Screening	Screening	Date of informed consent
PLACEBO/ BI 10773 10 MG	Placebo/Empa 10 mg	Treatment	Date of first administration of double-blind study treatment
FOLLOW-UP	Post Pbo/Post Empa	Follow up	Date of last administration of study drug + 1 day

Details on the definition of the treatment period for different endpoints are listed in [Table 6.1:2](#). The efficacy analyses will follow the intention-to-treat (ITT) principle. For the assignment of patients to treatment groups this means that patients will be analysed as randomised.

For safety analyses, patients will be also assigned to the treatment groups as randomised.

If a patient erroneously receives the wrong trial drug, all future medication packs will be dispensed as scheduled for the treatment group to which the patient was randomised. Therefore, the adverse events will be analysed as per randomised treatment, which is expected to reflect the prevailing treatment. In exceptional cases that a patient took the wrong treatment, all adverse events that occur while being on the wrong treatment will be listed and analyses of this data are described in [section 7.8.1.6](#).

Table 6.1: 2 Endpoint-specific assignment to the on-treatment phase

Endpoint	Last day of assignment to on-treatment phase (days after last intake of study medication)
6MWT distance	1
PRO endpoints (key secondary endpoints)	7
Adverse events	7
Safety laboratory measurements	3
Heart rate	1
Body weight	1
Creatinine and estimated glomerular filtration rate (eGFR)	1
Blood pressure	1

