## 6.7 BASELINE, TIME WINDOWS AND CALCULATED VISITS

For serum creatinine and values based upon this measurement such as eGFR, baseline will be defined as the mean of all available measurements from the screening visit until start of randomised trial medication. For all other endpoints, baseline will be defined as the last available measurement before start of randomised trial medication.

Since the protocol specifies that all measurements are taken at visit 2 before any intake of trial medication, all measurements at the first day of drug intake are assumed to qualify as baseline measurements. For laboratory values, clock time is recorded. If a lab measurement is done after treatment start, this will not qualify as baseline measurements, except in case of HbA1c, which is considered to be a stable measurement and qualifies for baseline on the whole day of first treatment intake.

For randomised patients without any treatment intake: For serum creatinine and values based upon this measurement such as eGFR, baseline will be defined as the mean of all available measurements from the screening visit until and including the day of randomisation. For all other endpoints, baseline will be defined as the last available measurement before or on the day of randomisation.

Medication taken at baseline is any medication with start date continued or before date of first study medication intake (randomisation for patients not treated) and end date continued or on or after date of first medication intake (randomisation for patients not treated).

Measurements taken after the first intake of randomised trial medication will be considered on-treatment values if they have been obtained up to end of the parameter specific follow-up period as defined in [Table 6.7: 1](#) below and will be assigned to the randomised study drug for efficacy and safety analyses.

Measurements taken after the end of the endpoint specific follow-up period after the last intake of study drug will be considered post-treatment values.

On-treatment (for OC-OT analysis) or all post-randomisation (for OC-AD analysis) efficacy and safety measurements will be assigned to visits based on time windows around the planned visit dates. These time windows are defined based on the planned number of days after the date of first administration of study drug.

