#### Acute renal failure

A frequency table of patients with AEs related to acute renal failure by treatment, primary SOC and preferred term will be provided based on the narrow SMQ Acute renal failure (20000003).

SAEs and AEs leading to discontinuation based on the narrow SMQ Acute renal failure (20000003) will be presented.

In addition, frequency tables will be produced for patients with elevated creatinine  $\geq 2$  x baseline and  $> 1$  x upper limit of normal (ULN).

Patients with acute renal failure will be listed.

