To support analyses of liver-related adverse drug effects, patients with Aspartate transaminase (AST) and/or Alanine transaminase (ALT)  $\geq 3 \times \text{ULN}$  with concomitant or subsequent Total Bilirubin (TBILI)  $\geq 2 \times \text{ULN}$  in a 30 day period after AST/ALT elevation are of special interest. In addition, of these cases, it will be considered whether the alkaline phosphatase (AP) is less than 2 x ULN (maximum value in a 30 day period after AST/ALT elevation) or not. The start of the 30-day time span is triggered by each liver enzyme elevation above the defined thresholds. Patients who fulfil one or two of the criteria for ALT/AST or total bilirubin elevations above and have no information available for the remaining parameter(s) within the 30 day time window will not be listed under “ALT and/or AST  $\geq 3 \times \text{ULN}$  with TBILI  $\geq 2 \times \text{ULN}$ ”.

In addition ALT/AST will be used to investigate elevated liver enzymes:

- ALT/AST  $\geq 3 \times \text{ULN}$
- ALT/AST  $\geq 5 \times \text{ULN}$
- ALT/AST  $\geq 10 \times \text{ULN}$
- ALT/AST  $\geq 20 \times \text{ULN}$

All liver enzyme elevations within 30 days of treatment discontinuation will be shown.

Frequency tables of patients with elevated liver enzymes defined by ALT and/or AST, total bilirubin and AP combinations will be provided. Details on patients with elevated liver enzymes will be listed.

For the following parameters:

- eGFR,
- creatinine (only descriptive),

the time course of changes will be assessed. The analysis will be performed by applying MMRM models to OC-OT data on the treated set. The MMRM models that will be used are specified in [Section 7.6](#). These analyses will be conducted on data before any normalisation. The MMRM analyses will also be shown graphically.

For the following parameters:

- haemoglobin, and
- haematocrit

the change from baseline will be assessed. The analysis will be performed by applying ANCOVA models to OC-OT data on the treated set. The ANCOVA model will include treatment and baseline as fixed effects. These analyses will be conducted on data before any normalisation.

To support analysis of renal function, eGFR throughout the trial will be categorised according to the following Chronic Kidney Disease (CKD) staging ([Table 7.8.2: 1](#)): All calculations for the staging of renal function will be based on the originally measured laboratory values, not on normalised values with BI standard reference ranges.

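### Creatinine drawn more than 1 day after the last dose counts as post-treatment, so the creatinine-defined renal AESI table can miss patients who stop early

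*SAP*

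**What the plan says.** **The window.** SAP 6.1, Table 6.1: 2, has a column headed "Last day of assignment to on-treatment phase (days after last intake of study medication". The row "Creatinine and estimated glomerular filtration rate (eGFR" carries the value 1. In the same table, other safety laboratory measurements have 3 and adverse events have 7. SAP 6.7 gives the consequence: "Measurements taken after the end of the endpoint specific follow-up period after the last intake of study drug will be considered post-treatment values". Table 6.7: 2 uses creatinine/eGFR as its example and moves such values to follow-up.

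**The AESI.** Protocol 5.2.7.1 defines it by a laboratory value only: "Decreased renal function is defined by a creatinine value showing a" rise to at least twice baseline, with the value also above ULN. It gives no time limit.

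**The planned renal outputs.** SAP 7.8.1.3 (Acute renal failure) plans tables of AEs, SAEs and AEs leading to discontinuation from the narrow SMQ, and a patient listing. It then adds: "In addition, frequency tables will be produced for patients with elevated creatinine" at or above twice baseline and above ULN. No window is stated for that table. SAP 7.8.2 takes creatinine and eGFR out of the standard laboratory tables and plans an eGFR shift table to the last and the lowest on-treatment value.

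**The comparators.** The AE residual effect period is "a period of 7 days after the last dose of trial medication" (Protocol 7.3.4; SAP 7.8.1.1 applies the same 7 days). For the liver, SAP 7.8.2 is explicit: "All liver enzyme elevations within 30 days of treatment discontinuation will be shown".

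**The visit.** Under Flow Chart footnote 11, patients who stop early "will be required to return to the study site as soon as possible after treatment discontinuation for the early discontinuation visit". No maximum number of days is given.

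**The concern.** A 1-day limit suits an analysis of mean eGFR over time, because it keeps off-drug recovery out of the estimate. Counting patients who ever reach a threshold is a different task. There, the sample taken just after a patient stops may be the one that shows the event.

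After baseline, creatinine is scheduled at day 43, day 85, early discontinuation and follow-up. For a patient who stops between visits, the early discontinuation sample may be the only scheduled one near the event. If it is drawn 2 or more days after the last dose, the general rule makes it post-treatment.

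At stake is whether the one summary built on the protocol's own AESI definition gives a fair between-arm frequency. The patients it can miss have stopped drug, some of them possibly because of the renal event. Any undercount would be larger in whichever arm has more such stops.

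**Working it through.** The plan gives no calculated figure to reproduce. The check is a classification of samples by day, followed by an illustration of size.

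**1. A sample drawn d days after the last dose** (SAP Table 6.1: 2, 7.8.1.1 and 7.8.2)

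| d | Creatinine/eGFR (1 day) | Other safety lab (3 days) | AE (7 days) | Liver enzymes (30 days) |
|---|---|---|---|---|
| 0–1 | counted | counted | counted | counted |
| 2–3 | post-treatment | counted | counted | counted |
| 4–7 | post-treatment | post-treatment | counted | counted |
| 8–30 | post-treatment | post-treatment | post-treatment | counted |

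The gap is d = 2 to 7: an AE with onset then is on-treatment, but a creatinine value drawn on the same day is not.

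**2. Who falls in the gap.** Protocol 4.1.4 asks patients to dose on the morning of visit 4. A completer who does so is sampled at d = 0 and is always inside the window. The gap therefore affects patients who stop early.

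**3. Which displays are affected**
- *Creatinine table, SAP 7.8.1.3.* No window of its own. The 3-day laboratory rule does not supply one, because Table 6.1: 2 gives creatinine its own row. The general 1-day rule is what remains, by inference.
- *Lowest-eGFR shift table, SAP 7.8.2.* Expressly on-treatment, so the 1-day limit applies directly.
- *SMQ-based AE, SAE and discontinuation tables.* The 7-day rule applies, so the patient is counted if the event is reported and codes to the narrow SMQ.
- *Listings.* All individual laboratory data are listed.
- *Follow-up summary of creatinine and eGFR, SAP 7.8.2.* Descriptive, and limited to patients with baseline, on-treatment and follow-up values. Someone who stops before visit 3, is sampled at d ≥ 2 and has no unscheduled earlier sample has no on-treatment value and is left out.

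**4. Size, as illustration only.** Neither input below is in the documents. Let p be the share of an arm of 150 reaching the criterion, assumed 1% to 4%. Let q be the share of those whose first qualifying value comes after day 1, assumed 10% to 50%.

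Expected cases = 150p; expected missed = 150pq; P(at least one missed) = 1 − (1 − pq)^150.

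| p | q | Expected cases per arm | Expected missed per arm | P(at least one missed) |
|---|---|---|---|---|
| 1% | 10% | 1.5 | 0.15 | 1 − 0.999^150 = 14% |
| 2% | 25% | 3.0 | 0.75 | 1 − 0.995^150 = 53% |
| 4% | 50% | 6.0 | 3.0 | 1 − 0.98^150 = 95% |

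**5. Effect of a 7-day window.** It would count every early discontinuation sample taken within a week of the last dose. The follow-up visit falls 7 to 14 days after the last dose (Protocol 6.2.3), so a strict 7-day cut would include a follow-up sample on day 7 and exclude one on days 8 to 14.

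**The case against.** The other side has several good points.

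- **The exclusion from the creatinine table is inferred.** SAP 7.8.1.3 does not restrict that table to on-treatment values. This stands, but the SAP offers no other window for creatinine, so the text needs completing either way. For the eGFR shift table no inference is needed.
- **The patient is not lost from renal reporting.** A reader might infer that someone who stops for renal injury disappears from every renal count. The documents do not support that: the SMQ-based tables, including the one for AEs leading to discontinuation, use 7 days, and the values are listed. What remains is that the AE tables depend on reporting and coding, and a listing gives no frequency by arm.
- **A qualifying value may already exist.** If a sample on drug or within 1 day of the last dose met the criterion, the patient is counted. Only a *first* qualifying value at day 2 or later is at risk.
- **The early discontinuation sample may be day 0.** Protocol 4.1.4 says treatment ends on the day of that visit, whereas Protocol 3.3.4.1 and the Flow Chart place the visit after stopping. These passages must be reconciled. The SAP clock runs from last intake, so the gap exists whenever the last tablet was taken 2 or more days earlier.
- **Creatinine's window is not uniquely short.** A reader might take it for the shortest in the plan, but 6MWT distance, heart rate, body weight and blood pressure also have 1 day. Endpoint-specific windows are a declared convention.
- **Safety analyses are descriptive** (Protocol 7.3.4). No confirmatory conclusion depends on this.

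**Conclusion.** The point holds in a limited form. Under the SAP's general rule, a first qualifying creatinine drawn 2 or more days after the last dose can be missed in the only summary that uses the protocol's AESI definition. Such a sample is also outside the lowest on-treatment eGFR shift table.

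This rests on two conditions: that the general window governs the SAP 7.8.1.3 creatinine table, and that no earlier sample already qualified.

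The number affected cannot be derived, because the documents give neither a rate of creatinine doubling nor the delay from last dose to the early discontinuation visit. The assumed ranges above give 0.15 to 3.0 patients per arm, so probably a few at most. A reader might want to quote a percentage of cases lost, but any such figure would restate assumptions.

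The loss falls on early stoppers and is therefore informative. Its direction between arms depends on which arm has more such stops, which the documents do not show. This is a cheap improvement to the safety displays.

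**What to change.** Keep the 1-day window for the creatinine and eGFR time-course analyses (OC-OT) and for the existing on-treatment eGFR shift table. For event counting, choose one of two changes:

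1. State a window for the SAP 7.8.1.3 creatinine table and set it to the 7-day AE residual effect period, for example as a second creatinine row in Table 6.1: 2.
2. Add a version of that table, and of the lowest-eGFR shift table, using all post-baseline values including early discontinuation and follow-up samples.

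The second avoids splitting follow-up visits at day 7 and leaves the on-treatment displays as they are.

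The cost is a short SAP edit and either one programming parameter or two added tables. Efficacy analyses are untouched. The small downside is that some off-drug values enter these displays, including completers' follow-up samples (under the first change, only those drawn by day 7), so the table titles should say so.

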## 6.2 IMPORTANT PROTOCOL DEVIATIONS

A protocol deviation (PD) is important, if it affects the rights or safety of the study patients or if it can potentially influence the primary outcome measures for the respective patients in a way that is neither negligible nor in accordance with the study objectives.

Important protocol deviations (iPDs) will be described in the clinical trial report (CTR). A listing of patients with medication code broken will be provided.

Table 6.2: 1 Important protocol deviations

Category / Code	Description	Requirements	Excluded from
A	Entrance criteria not met		
A1	Target indication not met		
A1.06	No chronic HF or no NYHA class II-IV	Inclusion criterion #5 not met	None
A1.07	Conditions on ejection fraction (EF) not met	Inclusion criterion #6 not met	None
A1.08	Conditions on NT-proBNP not met	Inclusion criterion #7 not met	None

Table 6.2: 1 Important protocol deviations (cont.)

Category / Code	Description	Requirements	Excluded from
A2/3	Other entrance criteria not met		
A2.02	Age out of range	Inclusion criterion #1 not met	None
A2.08	Specific inclusion criterion for women of child-bearing potential not met	Inclusion criterion #2 not met	None
A2.14	6MWT distance above 350m at screening or baseline or below 100m at baseline	Inclusion criterion #4 or exclusion criterion #10 not met	SensRS1
A2.12	Inclusion criterion on stable concomitant medication not met	Inclusion criterion #8 not met	None
A2.13	Use of medical devices not appropriate or device implanted recently or intent to implant	Inclusion criterion #10 or exclusion criterion #18 not met	None
A3.44	Patient with unstable conditions	Exclusion criteria #1, #2, #6, #9, #13, #17, #20, #21 or #25 not met, inclusion criterion #9 not met	None
A3.49	Participation in another Empagliflozin HF trial	Exclusion criterion #3 not met	None
A3.51	Type 1 diabetes	Exclusion criterion #4 not met	None
A3.09	Renal insufficiency or renal impairment (assessed by eGFR)	Exclusion criterion #5 not met	None
A3.33	Systolic blood pressure at visit 1 or 2 out of range	Exclusion criterion #7 not met	None
A3.31	Atrial fibrillation or atrial flutter with a resting heart rate >110bpm	Exclusion criterion #8 not met	None
A3.48	Presence of condition that precludes exercise testing	Exclusion criterion #11 not met	None
A3.47	Participation in structured Exercise training	Exclusion criterion #12 not met	None
A3.28	Currently implanted left ventricular assist device (LVAD)	Exclusion criterion #14 not met	None
A3.29	Patients with cardiomyopathies excluded by the protocol	Exclusion criterion #15 or #19 not met	None
A3.30	Any severe (obstructive or regurgitant) valvular heart disease excluded by the protocol	Exclusion criterion #16 not met	None
A3.06	Indication of liver disease	Exclusion criterion #22 not met	None
A3.34	Haemoglobin at visit 1 below cut-off	Exclusion criterion #23 not met	None
A3.35	History of Ketoacidosis	Exclusion criterion #24 not met	None

Table 6.2: 1 Important protocol deviations (cont.)

Category / Code	Description	Requirements	Excluded from
A3.36	Gastrointestinal (GI) surgery or GI disorder that could interfere with study medication absorption in the investigator's opinion	Exclusion criterion #26 not met	None
A3.37	Documented or active malignancy	Exclusion criterion #27 not met	None
A3.39	Intake of restricted medications or any drug considered likely to interfere with the safe conduct of the trial	Exclusion criterion #28 not met	None
A3.40	Treatment with any SGLT-2 inhibitor or SGLT-1 and 2 inhibitor	Exclusion criterion #29 not met	None
A3.50	Treatment with i.v. iron therapy or erythropoietin (EPO) within 3 months prior to screening	Exclusion criterion #30 not met	None
A3.11	Intake of an investigational drug in another trial within 30 days prior to intake of study medication in this trial	Exclusion criterion #31 not met	None
A3.41	Known allergy or hypersensitivity to empagliflozin	Exclusion criterion #32 not met	None
A3.13	Relevant alcohol or drug abuse and other conditions affecting study compliance	Exclusion criterion #33 not met	None
A3.12	Specific exclusion criterion for pre-menopausal women not met	Exclusion criterion #34 not met	None
A3.14	Any other clinical condition unsafe for participation that would jeopardise patient safety while participating in this clinical trial	Exclusion criterion #35 not met	None
B	Informed consent		
B1	Informed consent not available/not done	Informed consent date missing	All
B2	Informed consent too late	Informed consent date <actual consent date> was after Visit 1 date <Visit 1 date>	None

Table 6.2: 1 Important protocol deviations (cont.)

Category / Code	Description	Requirements	Excluded from
C	Trial medication and randomisation		
C1.02	Incorrect trial medication taken	Wrong medication taken for more than 20% of the overall treatment duration. Can only be finally judged after data base lock (DBL) since unblinding information is required.	None
C3.01	Non-compliance with study drug intake	Compliance <80% or >120%	None
C4.01 	Medication code broken inappropriately	Medication code was broken for no valid reason.  Final decision at the DBL meeting based on medical judgement.	None
D	Concomitant medication		
D2.01	Prohibited medication use	Review of eCRF for prohibited medication.  Final decision at the DBL meeting based on medical judgement.	None
G	Study-specific analysis		
G3.48 	Unsuitable set up or conduct for 6MWT at baseline or week 12	Important deviations from the set-up or conduct as defined in the protocol	SensRS1
G3.49 	Not compliant with contraindications of the 6MWT	6MWT not stopped when it should have been based on stopping criteria, 6MWT not rescheduled appropriately when patient presents with relative contraindications	SensRS1
G3.50 	Assessment order not followed that could influence PRO at baseline or week 12	PRO measurements not before any other assessment at baseline or week 12	None
I	Other safety-related deviations		
I2.01	Pregnancy		None

KEY: 6MWT= six minute walk test, HF=Heart Failure, NT-proBNP=N-Terminal Pro-Brain Natriuretic Peptide, NYHA= New York heart association, EF=ejection fraction, T1DM=Type 1 diabetes mellitus, bpm=beats per minute.

 needs to be checked at site by Local Clinical Monitors (CMLs) / Clinical Research Associates (CRAs) as these cannot be checked programmatically

